## 16.4 Sensitivity Analysis Including Data from Site(s) with Data Quality Issues

For Site 114 excluded for data quality issues, sensitivity analysis will be performed including data on the primary efficacy endpoint.

For the patients from Site 507 excluded for primary efficacy source data unavailable or unreliable data, sensitivity analysis will be performed including data on the primary efficacy endpoint.

Variable	Analysis set	Analysis type
Change in mean sitting SBP between Visit 2 (Week 0) and Visit 5 (Week 12)	mITT including all patients (all patients from Site 114 and Site 507)	Paired t-test

In the case of a significant difference between the results of the two primary efficacy analyzes (mITT vs. mITT including all patients), the efficacy outcome (primary, secondary and exploratory) variables will be analyzed using both the mITT as well as the "mITT including all patients" population. All results of the "mITT including all patients" analysis will be reported in the CSR.

Data from Site 114 and from those patients from Site 507 for whom primary efficacy data are unavailable or unreliable will not be excluded from the safety analysis.

## 17. QUALITY OF LIFE ANALYSIS

Not applicable.

Page 34 of 46

## 18. SAFETY OUTCOMES

All outputs for safety outcomes will be based on the Safety Analysis Set. The primary safety endpoint will be summarized with counts and percentage of patients reporting any TEAEs and patients with at least one or any TEAE with corresponding 95% CI using exact binomial method, with two-sided p-value will be presented.

#### 18.1. Adverse Events

Adverse Events (AEs) will be coded using Medical Dictionary for Regulatory Activities (MedDRA) central coding dictionary, Version 26.0 or latest.

Treatment emergent adverse events (TEAEs) are defined as new AEs that occur on or after the date/time of the first administration of study medication (i.e., monotherapy and/or combination therapy) or worsen if an AE started prior to the start of first administration of study medication. TEAEs that occurred or worsened on or after the date/time of the first administration of Monotherapy but before the date/time of the first administration of Combination Therapy will be summarized under "Monotherapy".

TEAEs that occurred or worsened on or after the date/time of the first administration of Combination Therapy will be summarized under "Combination Therapy".

Related Adverse Events: adverse events with relationship to study treatment (as recorded on the AE eCRF page, Relationship with study treatment = Related) reported by the investigator and those of unknown relationship (i.e. no answer to the question "Relationship with study treatment"). all AEs occurred after the study drug intake (monotherapy and/or combination), regardless of the causality relationship (related or not-related), have to be reported in AE pages of eCRF and should be managed.

Serious Adverse Events (SAE): serious adverse events (as recorded on the AE eCRF page, Serious Adverse Event = Yes).

Adverse Events Leading to Treatment Discontinuation: adverse events leading to permanent discontinuation of study treatment (as recorded on the AE eCRF page, Action taken with study treatment = Drug withdrawn).

See APPENDIX 2 for handling of partial dates for AEs. In the case where it is not possible to define an AE as treatment emergent or not, the AE will be classified by the worst case, i.e., treatment emergent.

An overall summary of number of patients within each of the categories described in the subsection below, will be provided as specified in the templates.

Listings will include TEAEs and Non-TEAEs.

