FORM-000050125	3.0, CURRENT	Effective	13 May, 2022

[figure not shown]
	Patients with uncontrolled BP levels (sitting BP \geq 130/80 mmHg in patients < 65 years old/sitting BP \geq 140/80 mmHg in patients \geq 65 years old) at Visit 2, with adequate treatment adherence (ranging between 80% to 120%) and who did tolerate the treatment, will enter into the Assessment period and will be assigned to the extemporaneous combination of NEB/RAM 5/2.5 mg. Patients with controlled BP levels (sitting BP < 130/80 mmHg in patients < 65 years old/sitting BP < 140/80 mmHg in patients \geq 65 years old) and/or who do not tolerate the treatment or have an adherence range below 80% or above 120%, will be withdrawn from the study (drop-out patients).
	After 4 weeks \pm 2 days in the Assessment period (Week 4), patients BP will be further evaluated at Visit 3: patients with controlled BP levels (sitting BP < 130/80 mmHg in patients < 65 years old/sitting BP < 140/80 mmHg in patients \geq 65 years old) will continue the same extemporaneous combination, while patients with uncontrolled BP levels (sitting BP \geq 130/80 mmHg in patients < 65 years old/sitting BP \geq 140/80 mmHg in patients \geq 65 years old/sitting BP \geq 140/80 mmHg in patients \geq 65 years old/sitting BP \geq 140/80 mmHg in patients \geq 65 years old) will be up-titrated from NEB/RAM 5/2.5 mg to NEB/RAM 5/5 mg for further 4 weeks \pm 2 days.
	 After further 4 weeks ± 2 days (Week 8) the BP will be assessed again (Visit 4): controlled patients will continue the same extemporaneous combination, while uncontrolled patients: if on NEB/RAM 5/2.5 mg, will be up-titrated to NEB/RAM 5/5 mg for further 4 weeks ± 2 days (Visit 5, Week 12); if on NEB/RAM 5/5 mg, will be up-titrated to NEB/RAM 5/10 mg for further 4 weeks ± 2 days (Visit 5, Week 12).
	At the end of the Assessment period (12 weeks \pm 2 days) at Visit 5, the antihypertensive effect of the extemporaneous combination (NEB/RAM 5/2.5 mg, NEB/RAM 5/5 mg or NEB/RAM 5/10 mg) will be evaluated. First Patient In: estimated by September 2023
	Last Patient Out: estimated by April 2024
Patient Study Phases Duration	 For patients completing the study, participation will last up to 16 weeks: 4 weeks of Run-in period (monotherapy) 12 weeks of Assessment period (extemporaneous combination)

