• To evaluate the safety and tolerability of the monotherapies (NEB 5 mg and RAM 5 mg) and of the extemporaneous combinations (NEB/RAM 5/2.5 mg, NEB/RAM 5/5 mg, NEB/RAM 5/10 mg).	 Safety and tolerability of the monotherapies (NEB 5 mg and RAM 5 mg) and of the extemporaneous combination (NEB/RAM 5/2.5 mg, NEB/RAM 5/10 mg) measured by incidence, intensity (severity), seriousness of Adverse Events (AEs) during the study period, (screening, Run-in period and Assessment period), relationship to the study treatments, clinically significant abnormal change in vital signs, electrocardiogram (ECG), laboratory parameters and use of concomitant medications at Visit 2 (Week 0), Visit 3 (Week 4), Visit 4 (Week 8) and Visit 5 (Week 12). 	• Incidence of adverse drug reactions (ADRs), AEs, serious adverse events (SAEs), needs to be studied to address safety and tolerability of the extemporaneous combination.
Exploratory		
• To assess the antihypertensive efficacy of the extemporaneous combination of NEB 5 mg with RAM 2.5/5/10 mg by evaluating the patients who achieved the standard BP goal (sitting BP < 140/90 mmHg) at Visit 2 (Week 0), at Visit 3 (Week 4) and at Visit 4 (Week 8).	• Number and proportion of patients achieving the standard BP goal (sitting BP < 140/90 mmHg) at Visit 2 (Week 0), Visit 3 (Week 4) and Visit 4 (Week 8).	• The proportion of patients achieving the target is a very important clinical indicator of therapeutic success. ¹⁹
• To assess the antihypertensive efficacy of the extemporaneous combination of NEB 5 mg with RAM 2.5/5/10 mg by evaluating the patients who achieved the optimal BP goal (sitting BP < 130/80 mmHg in patients < 65 years	 Number and proportion of patients achieving the optimal BP goal (sitting BP < 130/80 mmHg in patients < 65 years old/sitting BP < 140/80 mmHg in patients ≥ 65 years old) at Visit 2 (Week 0), Visit 3 (Week 4), and Visit 4 (Week 8). 	• The proportion of patients achieving the target is a very important clinical indicator of therapeutic success. ¹⁹

MENARIN	Global Medical Department		
	Protocol Template		
Identification Number	Version Number State Effective date		
FORM-000050125	3.0, CURRENT	Effective	13 May, 2022

OBJECTIVES	ENDPOINTS	JUSTIFICATION FOR ENDPOINTS
old/sitting BP < 140/80 mmHg in patients ≥ 65 years old) at Visit 2 (Week 0), at Visit 3 (Week 4), and at Visit 4 (Week 8).		

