To evaluate the safety and tolerability of the monotherapies (NEB 5 mg and RAM 5 mg) and of the Extemporaneous combinations (NEB/RAM 5/2.5 mg, NEB/RAM 5/10 mg).	Safety and tolerability of the monotherapies (NEB 5 mg and RAM 5 mg) and of the extemporaneous combination (NEB/RAM 5/2.5 mg, NEB/RAM 5/5 mg, NEB/RAM 5/10 mg) measured by incidence, intensity (severity), seriousness of Adverse Events (AEs) during the study period, (screening, Run-in period and Assessment period), relationship to the study treatments, clinically significant abnormal change in vital signs, electrocardiogram (ECG), laboratory parameters and use of concomitant medications at Visit 2 (Week 0), Visit 3

Page 11 of 46

(Week 4), Visit 4 (Week 8) and Visit 5 (Week
[12].

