## 14. STUDY MEDICATION EXPOSURE

Exposure to study medication for both Monotherapy and Combination therapy in days will be presented for the SAF population.

The date of first study medication administration will be taken from the eCRF "Exposure" form. The date of last study medication will be taken from the eCRF "End of Study Treatment" form. Interruptions, Adherence, and dose changes are not taken into account for duration of exposure.

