#### 14.1. Derivations

Duration of exposure (days) = date of last study medication administration – date of first study medication administration + 1.

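### TEAEs are reported as crude patient percentages over about 4 weeks of monotherapy and 12 weeks of combination, with no patient-time measure and no dose-at-onset rule; separately, monotherapy exposure has no stated end date

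*SAP*

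**What the plan says.** The secondary safety objective in Protocol section 4 is "To evaluate the safety and tolerability of the monotherapies (NEB 5 mg and RAM 5 mg) and of the extemporaneous combinations", followed by the three combination strengths. SAP 2.2 repeats it. Five treatments are therefore named.

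SAP 18 summarises TEAEs as counts and percentages of patients with an exact binomial interval, and adds a two-sided p-value without saying what it compares. SAP 18.1.2 shows that its incidence rates are frequencies and percentages, and SAP 7 bases percentages on numbers of patients. No events per unit of time are planned.

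SAP 18.1 divides events by date. Those starting or worsening from the first monotherapy dose until the first combination dose are Monotherapy. "TEAEs that occurred or worsened on or after the date/time of the first administration of" combination therapy are all Combination Therapy, whatever ramipril dose was being taken. In Appendix 1, listings are ordered by these two groups, but the table of treatment groups for tables, listings and figures has five: NEB 5, RAM 5, and NEB 5 with RAM 2.5, 5 or 10.

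On exposure, SAP 14 presents days for both phases but gives one source for the end date: "The date of last study medication will be taken from the eCRF 'End of Study Treatment' form". It adds: "Interruptions, Adherence, and dose changes are not taken into account for duration of exposure". The formula in SAP 14.1 is "Duration of exposure (days) = date of last study medication administration" minus the date of first administration, plus 1.

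**The concern.** The combination phase is three times as long as the run-in. A crude percentage rises with observation time, so the combination column will show more patients with events even if the drugs carry the same hazard. No formal safety comparison between phases is named, but the two columns will be read side by side, and an unexplained p-value invites that reading.

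Within combination, the objective names each dose, yet nothing says how an event enters a dose column or who forms that column's denominator. Patients spend different lengths of time at each dose, and one patient can belong to up to three dose columns. The five-group layout in Appendix 1 cannot be filled from the SAP text alone.

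The exposure point is separate. Phase-specific and dose-specific days are what a patient-time rate would need, and SAP 14 supplies neither clearly.

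**Working it through.** The plan states no TEAE rate, safety sample size or safety power, so there is no figure of its own to reproduce here.

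**Inputs**
- Monotherapy run-in 4 weeks (28 days) and combination 12 weeks (84 days): Protocol synopsis, patient study phases. Visit windows of ±2 days are ignored.
- Up-titration only at Visits 3 and 4, driven by BP: Protocol section 5.
- 4-week risk *p* of a first TEAE: assumed, 2% to 30%, with a constant hazard that is the same under every treatment.

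**Step 1. Effect of unequal time.** Twelve weeks is three 4-week blocks, so the 12-week risk is 1 − (1 − *p*)³.

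| Assumed 4-week risk | 12-week risk | Ratio |
|---|---|---|
| 2% | 5.9% | 2.9 |
| 5% | 14.3% | 2.9 |
| 10% | 27.1% | 2.7 |
| 20% | 48.8% | 2.4 |
| 30% | 65.7% | 2.2 |

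With no true difference, the combination percentage would be 2.2 to 2.9 times the monotherapy percentage.

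**Step 2. The same data per patient-time.** At *p* = 10% the monotherapy rate is −ln(0.90)/4 = 0.0263 per week, or 2.63 first events per 100 patient-weeks. The combination rate is −ln(1 − 0.271)/12 = 0.0263 per week, also 2.63. The rate removes the time artefact.

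**Step 3. Time at each dose.** The titration rules allow four paths for a completer:
- 5/2.5 mg throughout: 12 weeks.
- 5/2.5 mg for 8 weeks, then 5/5 mg for 4.
- 5/2.5 mg for 4 weeks, then 5/5 mg for 8.
- 5/2.5, 5/5 and 5/10 mg for 4 weeks each.

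Time at 5/2.5 mg is thus 4 to 12 weeks; at 5/5 mg it is 4 or 8 weeks among those who reach it; at 5/10 mg it is 4 weeks among those who reach it. Crude percentages by dose would also cover unequal time.

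**Step 4. Monotherapy exposure.** If the End of Study Treatment date is applied to monotherapy as well, a completer's exposure is 28 + 84 = 112 days against 28 actual days: 112/28 = 4 times too long. A rate built on that denominator at *p* = 10% would be 100 × 0.1054/16 = 0.66 per 100 patient-weeks instead of 2.63.

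**The case against.** Several points can fairly be made for the plan.

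- **Dose groups exist in Appendix 1.** A reader might infer from SAP 18.1 that adverse events will not be shown by dose at all. The documents do not support that. Appendix 1 lists exactly the five treatments in the objective, and SAP 8 and 18.1 leave table layout to templates that are not among the documents. What stands is the conflict between two groups and five, and the missing attribution rule and denominators.
- **The monotherapy end date may be meant to be phase-specific.** A reader might infer that the SAP runs monotherapy exposure to the end of the study. It nowhere says so. SAP 18.1 closes the monotherapy period for events at the first combination dose, SAP 15.1 uses a treatment end date in its monotherapy adherence formula, and SAP 18.2 uses the End of Study Treatment form to identify deaths during monotherapy. What stands is that SAP 14 does not state the date and SAP 15.1 does not define it; 112 days is only the literal result.
- **Exposure is not the denominator of any TEAE table.** Correcting SAP 14 would change no planned percentage. It is a separate defect, relevant to rates if they are added.
- **Crude incidence does address the stated endpoint.** The protocol asks for incidence, severity and seriousness by treatment and names no contrast between phases. It would be too strong to say the objective goes unanswered. The figures are simply not comparable across columns of unequal length.
- **Events can be placed by hand.** Study Day counts from the first combination dose and appears in listings (SAP 6.1), and doses change only at scheduled visits. Events before and after up-titration can therefore be separated in listings, though no summary is specified to do it.
- **Time adjustment does not remove selection.** Only patients who tolerated the run-in, were adherent and remained uncontrolled enter combination, and dose then follows BP response. Some had taken the run-in drug for at least 30 days beforehand. The first 4 weeks of combination equal the run-in in length but not in population.

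**Conclusion.** The point holds in a limited form. TEAEs are planned as crude percentages in two bins of about 4 and 12 weeks, with no patient-time measure and no dose-at-onset rule, and the two-group and five-group texts need reconciling. The inflation of 2.2 to 2.9 times is illustrative: it rests on an assumed constant, equal hazard and on assumed 4-week risks. The undefined monotherapy end date is a separate gap, worth a factor of four only under the literal reading. This affects a named secondary objective and not the primary endpoint. It is worth correcting before the tables are run.

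**What to change.** In SAP 14 and 14.1, define exposure start and end dates for each phase and each combination dose, with monotherapy exposure ending the day before the first combination dose.

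In SAP 18.1:
- Assign each TEAE to the treatment and dose being taken at onset or worsening.
- Align the two-group text there and in the Appendix 1 listing order with the five groups in Appendix 1, and define each column's denominator as the patients who took that treatment.
- Beside the crude percentages, report all events per patient-time and first events per patient-time at risk.
- Optionally add a column for the first 4 weeks of combination, described as equal in length to the run-in and not as a like-for-like comparison.
- Label all rates descriptive, because of selection into combination and BP-driven titration.

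In SAP 18, state what the two-sided p-value compares, or drop it.

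The cost is SAP wording and modest extra programming. No new assessments are needed: new doses are dispensed at Visits 2 to 4 and first taken on site at the end of the visit (Protocol 5.1). The exception is home delivery under Protocol 7.2, where the first-intake date would have to come from the exposure record. The documents do not show whether the eCRF records each dose change as a date, so that should be confirmed first.

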#### 18.1.1. All TEAEs

Incidence of TEAEs will be presented by System Organ Class (SOC) and Preferred Term (PT) and broken down further by maximum severity and relationship to study medication (i.e., monotherapy and/or combination therapy).

Page 35 of 46

The following tables will be created:

The overall summary of AEs table will include the following categories:

- TEAEs
- Related TEAEs
- TEAEs leading to permanent treatment discontinuation
- Related TEAEs leading to permanent treatment discontinuation
- Serious TEAEs
- Related serious TEAEs
- TEAEs leading to death
- Related TEAEs leading to death

#### 18.1.1.1. SEVERITY

Severity is classed as mild/ moderate/ severe (increasing severity). TEAEs starting after the first dose of study medication (i.e., monotherapy and/or combination therapy) with a missing severity will be classified as severe. If a patient reports a TEAE more than once within that SOC/ PT, the AE with the worst-case severity will be used in the corresponding severity summaries.

#### 18.1.1.2. RELATIONSHIP TO STUDY MEDICATION

Relationship, as indicated by the Investigator, is classed as "Not Related", "Related" (increasing severity of relationship). A "related" TEAE is defined as a TEAE with a relationship to study medication (i.e., monotherapy and/or combination therapy) as "Certain Related", "Probable Related", "Probable Related" or "Unassessable" to study medication. TEAEs with a missing relationship to study medication will be regarded as "Probable Related" to study medication. If a patient reports the same AE more than once within that SOC/ PT, the AE with the worst-case relationship to study medication will be used in the corresponding relationship summaries.

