9.2 Drug Relationship

The relationship between an AE and study drugs will be judged according to the following categories:

- **Certain**: The AE occurs in a plausible time relation to the administration of the drug and cannot be explained by a concurrent disease or other drugs or chemicals. The response to withdrawal of the drug (dechallenge) should be clinically plausible. The event must be definitive pharmacologically or phenomenologically, using a satisfactory rechallenge procedure if necessary.
- **Probable:** The AE occurs in a reasonable time relation to the administration of the drug; it is unlikely to be attributed to a concurrent disease or other drugs or chemicals and it follows a clinically reasonable response on withdrawal (dechallenge).

REVARIN	Global Medical Department		
		Protocol Template	
Identification Number	Version Number	State	Effective date
FORM-000050125	3.0, CURRENT	Effective	13 May, 2022

Rechallenge information (AE reappearance after drug reintroduction) is not required to fulfill this definition.

- **Possible**: The AE occurs with a reasonable time relation to the administration of the drug, but it could also be explained by a concurrent disease or other drugs or chemicals. Information on drug withdrawal (dechallenge) may be lacking or unclear.
- **Unassessable:** The relationship cannot be judged, because of the information is insufficient or contradictory and cannot be supplemented or verified.
 - **Unlikely**: A causal relationship cannot be definitively ruled out, but:
 - other drugs, chemicals, or underlying disease provide plausible explanations and / or
 - the temporal relation to the administration of the drug makes a causal relation improbable.
- Not Related: Any of the following are present:
 - existence of a clear alternative explanation, and / or
 - unreasonable temporal relationship between Drug and Event, and / or
 - non-plausibility.

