9.3 Adverse Drug Reaction (ADR)

An ADR is any untoward and unintended response to an IMP related to any dose administered.

The definition implies a reasonable possibility of a causal relationship between the event and the IMP. This means that there are facts (evidence) or arguments to suggest a causal relationship.

An ADR is considered any AE for which the relationship is considered as:

- 1. Certain
- 2. Probable
- 3. Possible
- 4. Unassessable
- An AE is not considered as ADR when the relationship is judged as:
 - 1. Unlikely
 - 2. Not related

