9.9 Collection, Recording and Reporting of AEs

At each visit, the Investigator will collect and assess any subjective or objective AE occurred to each patient after his/her signature of the informed consent.

Any AE (or adverse experience) occurring prior to first IMP administration should be considered as medical history or pre-existing conditions and should be recorded on the Medical History/Pre-existing eCRF page and not on the AE page.

Any clinically significant laboratory test results observed after informed consent signature and prior to first IMP administration, should be recorded in Lab Test page of the eCRF, and must not be considered as an AE.

The Investigator should manage as AE any laboratory test abnormality (newly occurring after the IMP administration or worsening of previously known abnormalities) considered as clinically relevant: i.e., values significantly above or under normal range or which require an intervention or diagnostic tests or may result in the IMP discontinuation.

Any AE communicated by the patient or by the patient's relatives or delegates through phone calls, letters or e-mails will also be collected and assessed.

The Investigator shall record on the respective eCRF AE pages, any recognized AE identifying an ICSR, occurred after IMP administration, both serious and non-serious, whether or not thought to be drug-related, observed in or reported by the patient (or relatives/delegates), specifying the judgment on the causal relationship with the study treatment (monotherapy or extemporaneous combination).

Any available information and diagnostic measure (laboratory and instrumental tests, procedures, etc.) shall be recorded in and/or attached to the concerned CRF pages/sections. The Investigator is expected to also record any AE which was ongoing at the last treatment dose and a follow-up phone call should be made after 2 weeks from the last study visit. The Investigator is expected to follow up any AE occurred during the study, including the follow-up period, until the outcome of the AE has been determined.

The Investigator must report all the collected information on any ICSR with Serious and Non-Serious AE (whether or not thought to be related to the investigational drug), providing the concerned eCRF AE pages by alert e-mail, after the first knowledge of the occurrence of the case, to:

REVAINS	Glol	oal Medical Department	
	Protocol Template		

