## 1. Introduction

This statistical analysis plan (SAP) describes the rules and conventions to be used in the presentation and analysis of efficacy and safety data for Protocol MEIN/22/NeRam-Hyp/001. It describes the data to be summarized and analyzed, including specifics of the statistical analyses to be performed.

This SAP is based on protocol version 3.0, dated 13 July 2023.

The Inclusion and Exclusion criteria are detailed in the section 6.2 of the protocol.

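### The SAP's list of related adverse events names Probable twice and leaves out Possible, so it does not match Protocol 9.3

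*SAP*

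**What the plan says.** Protocol 9.2 sets the causality scale: "The relationship between an AE and study drugs will be judged according to the following categories". Six categories follow, in this order: Certain, Probable, Possible, Unassessable, Unlikely and Not Related. Possible has its own definition, separate from Probable.

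Protocol 9.3 divides the six. "An ADR is considered any AE for which the relationship is considered as" Certain, Probable, Possible or Unassessable. Unlikely and Not related are not adverse drug reactions. Protocol 9.7 refers to 9.3 for the meaning of drug-related. Under Protocol 9.9 the investigator records each event on the eCRF AE pages, "specifying the judgment on the causal relationship with the study treatment".

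The SAP states its source: "This SAP is based on protocol version 3.0, dated 13 July 2023". It defines a related event in two places.

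- **SAP 18.1.1.2.** There are two classes: "Relationship, as indicated by the Investigator, is classed as 'Not Related', 'Related". The related class consists of events rated "Certain Related', 'Probable Related', 'Probable Related' or 'Unassessable' to study medication". For unanswered ratings, "TEAEs with a missing relationship to study medication will be regarded as 'Probable Related' to study medication".
- **SAP 18.1.** Related events are those with the eCRF entry "Relationship with study treatment = Related) reported by the investigator and those of unknown relationship", meaning that the question was left unanswered.

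**The concern.** The SAP list has four entries but only three different categories, and Possible is not among them. Nothing marks this as a deliberate change: SAP 3.3, which summarises changes from the planned analysis, says nothing about causality.

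Relationship to study treatment is a named component of the secondary safety endpoint in Protocol 4, and the safety analysis in Protocol 12.5 calls for summaries of related events. The study is open-label and not randomised, and every patient who enters the Assessment period receives the combination. There is no concurrent control rate to compare with, so investigator-assessed causality carries more of the safety interpretation than it would in a controlled trial.

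An error here runs in one direction. Leaving a category out of the related class can lower related-event counts or leave them unchanged, but it cannot raise them.

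**Working it through.** There is no planned figure to reproduce. The check compares the category lists and follows the consequence into the tables.

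**Step 1. The two definitions side by side**

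| Rating (Protocol 9.2) | Protocol 9.3 | SAP 18.1.1.2, read literally |
|---|---|---|
| Certain | related | related |
| Probable | related | related (listed twice) |
| Possible | related | not in the related list |
| Unassessable | related | related |
| Unlikely | not related | not in the related list |
| Not related | not related | not related |
| No answer | not addressed | related |

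**Step 2. Count.** The protocol has 4 related and 2 not related categories, 6 in all. The SAP list has 4 entries, of which 4 − 1 = 3 are distinct. The protocol's related set minus the SAP's is {Possible}, one category. The SAP's minus the protocol's is empty. The SAP does not say in words that every unlisted rating is Not Related. That follows from having two classes and a closed list for one of them, and it gives a 3 / 3 split: Certain, Probable and Unassessable against Possible, Unlikely and Not related.

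**Step 3. Slip or intention.** The list follows the order of Protocol 9.3, and the second Probable stands in third place, where the protocol has Possible. Putting Possible there reproduces the protocol's list exactly. The literal rule also clashes with the SAP's conservative handling elsewhere: missing severity becomes severe (18.1.1.1), undeterminable treatment emergence becomes treatment-emergent (18.1), and a missing relationship becomes related (18.1.1.2). A rule that counts a blank as related but a Possible as not related does not fit that pattern.

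**Step 4. Does SAP 18.1 repair it?** No. It relies on an eCRF value of Related, or no answer, and does not say which of the six ratings make up Related.

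**Step 5. Reach.** The overview in SAP 18.1.1 has 8 rows, 4 of them related rows: related TEAEs, related TEAEs leading to permanent discontinuation, related serious TEAEs, and related TEAEs leading to death. The breakdown by system organ class and preferred term is also split by relationship. The overview counts patients, so, with the SAP's missing-value rule applied on both sides, for each related row:

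patients (literal SAP) = patients (protocol definition) − patients whose events qualifying for that row were all rated Possible.

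The subtracted number is zero or more. A patient who also had a qualifying event rated Certain, Probable or Unassessable, or left unrated, stays in the row. The documents give no events by causality rating, so the number cannot be filled in.

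**The case against.** The case for treating this as editorial has three parts.

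1. **Two conditions must hold together.** The analysis field must carry six categories, and a programmer must code a visibly repeated word literally. The eCRF and the table templates are not in the documents. SAP 18.1 quotes a field value of Related and speaks of events as related or not related, which may mean a binary field. In that case the overview rows could be derived without the faulty list.
2. **Placing Possible under Not Related is an inference.** The SAP never defines Not Related as everything left over. Strictly, Possible and Unlikely are both unmapped.
3. **Protocol 9.3 defines an adverse drug reaction, not a related TEAE.** The link to drug-related runs through 9.7, which concerns SUSARs.

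The first part stands as a limit on the effect: it may be nil. It does not remove the error, because Protocol 9.2 and 9.9 require a six-category judgement recorded on the eCRF AE pages, and SAP 18.1.1.2 itself lists graded ratings. A graded field is a realistic possibility.

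The second stands as a caution on wording. Whichever class Possible falls into by default, the list does not count it as related. The third changes little: the SAP borrows the protocol's scale and matches 9.3 in every entry but one.

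Whether the listings would be affected is open, because the SAP does not say if they show the raw rating or a derived flag.

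**Conclusion.** The concern holds. SAP 18.1.1.2 omits Possible from the related class and so departs, undeclared, from Protocol 9.3. One category of six is misplaced, and confidence in that is high because it is read directly from the two lists. That it is a slip is an inference, though a strong one.

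The consequence is conditional. With a six-category eCRF field and literal programming, 4 of 8 overview rows and the relationship breakdown would understate related events or leave them unchanged. With a binary field there may be no effect. The size cannot be computed and may be zero. The overview rows not restricted to related events (all, discontinuation, serious, death), SUSAR reporting and the efficacy analyses do not depend on this list.

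It should be corrected: it is an operative rule for a component of the secondary safety endpoint, and a programmer should not have to guess what the second Probable means.

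**What to change.** In SAP 18.1.1.2, replace the second *Probable Related* with *Possible Related*. State the whole mapping so that nothing is left to inference: related is Certain, Probable, Possible or Unassessable; not related is Unlikely or Not related; a missing rating stays counted as related.

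In SAP 18.1, define related adverse events by reference to that mapping. If the eCRF field turns out to be binary, say so there, and state that the eCRF value Related stands for the four ratings in Protocol 9.3. Then check the derivation against the corrected text.

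The cost is one phrase and one line of mapping in 18.1.1.2, one aligned sentence in 18.1, and a programming check. No new rule is introduced, since this restores the protocol's own definition. Related-event rates may come out higher than under the literal text; by how much is unknown.
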